9.6 Post-surgery Follow-Up Visit (2-6 weeks following surgery)

Subjects with bulky residual adenopathy such that resection was not attempted will be removed from protocol therapy and should receive standard oncology care as deemed appropriate by the treating physician.

Subjects with positive surgical margins or N2 disease will be removed from protocol and considered for standard of care post-operative radiation +/- standard chemotherapy as deemed appropriate by their physician. Subjects who are completely resected or who refuse or cannot receive adjuvant chemotherapy will be given the option of receiving adjuvant Pembrolizumab.

- Vital signs (temp, B/P, pulse)
- Weight
- ECOG performance status
- Physical exam
- Routine blood work
- Adverse events assessment*
- **Research blood sample (3rd collection).** Research blood: blood will be collected to assess longitudinal analyses of T cell and MDSC phenotypes and blood based biomarkers. 4 tubes of 8.5-ml each will be collected. The tubes used will be ACD anti-coagulated Vacutainer (yellow tops). Samples will be collected and transported/shipped to the Substrate Services Core lab for processing. This blood sample to be collected 2-6 weeks after surgery and prior to adjuvant therapy (Refer to Appendices F and G).

*All AEs that occur prior to the Safety Follow-Up Visit should be recorded. Subjects with an AE of grade > 1 will be followed until the resolution of the AE to grade 0-1 or until the beginning of a new anti-neoplastic therapy, whichever occurs first. SAEs that occur within 90 days of the end of treatment or before initiation of a new anti-cancer treatment should also be followed and recorded.

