9.8 Adjuvant Pembrolizumab

Following completion of all standard adjuvant therapy, including chemotherapy and/or radiation therapy, patients will receive 4 cycles of pembrolizumab 200 mg every 21 days. Patients who receive both adjuvant CT plus adjuvant RT should start Pembrolizumab within 8 months of surgery. Patients who receive only one modality of adjuvant therapy (e.g. CT alone or RT alone) should start Pembrolizumab within 6 months of surgery. Patients who do not receive any adjuvant therapy should start Pembrolizumab within 4 months of surgery

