11.1 Treatments Administered

Patients will receive pembrolizumab as follows:**

Neoadjuvant Pembrolizumab: Cycle 1 day 1: pembrolizumab 200 mg IV

Cycle 2 day 1 (21 days after cycle 1 day 1): pembrolizumab 200 mg IV

Pembrolizumab will be administered as a 30-minute IV infusion (treatment cycle may be delayed up to 3 weeks due to toxicity). Sites should make every effort to target infusion timing to be as close to 30 minutes as possible. However, given the variability of infusion pumps from site to site, a window of -5minutes and +10 minutes is permitted (i.e., allowed infusion time is between 25 and 40 minutes).

Surgery: Standard surgical evaluation to occur after the last dose of pembrolizumab followed by surgical therapy.

Adjuvant chemotherapy: Is a standard consideration as per NCCN guidelines. Patients will be evaluated and offered adjuvant chemotherapy based on standard criteria such as T > 3 cm and/or metastases in N1 and/or N2 lymph nodes. Adjuvant chemotherapy is not study specific and should be given by commercial supply and standard of care.

Adjuvant radiation: Is sometimes a standard consideration as per NCCN guidelines. Patients will be evaluated and offered radiation based on standard criteria such as positive post-operative tumor margin and/or presence of metastases in N2 lymph nodes. Adjuvant radiation is not specific to this study and should be given as per standard of care.

Adjuvant Pembrolizumab: Three to 6 weeks after completion of all standard therapy including adjuvant chemotherapy and/or radiation therapy, patients will receive pembrolizumab 200 mg IV every 21 days for 4 doses.

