13.2 Prohibited Concomitant Medications

Subjects are prohibited from receiving the following therapies during the Screening and Treatment Phase of this trial:

- Antineoplastic systemic chemotherapy or biological therapy
- Immunotherapy not specified in this protocol
- Chemotherapy not specified in this protocol
- Investigational agents other than pembrolizumab
- Radiation therapy other than post-operative radiation for lung cancer
- Live vaccines within 30 days prior to the first dose of trial treatment and while participating in the trial. Examples of live vaccines include, but are not limited to, the following: measles, mumps, rubella, varicella/zoster, yellow fever, rabies, BCG, and typhoid vaccine.
- Systemic glucocorticoids for any purpose other than to modulate symptoms from an event of clinical interest of suspected immunologic etiology. The use of physiologic doses of corticosteroids may be approved after consultation with the Sponsor.

Subjects who, in the assessment by the investigator, require the use of any of the aforementioned treatments for clinical management should be removed from the trial. Subjects may receive other medications that the investigator deems to be medically necessary.

The Exclusion Criteria describes other medications which are prohibited in this trial. There are no prohibited therapies during the Post-Treatment Follow-up Phase.

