- The patient, for any reason, requires treatment with another systemic agent potentially effective for treatment of the study indication. In this case, discontinuation from the study occurs immediately upon introduction of the new agent.
- A patient who cannot be administered the study drug after a 21-day delay must be discontinued from the study treatment.
- A patient with bulky residual adenopathy such that resection is not attempted will be removed from protocol therapy and should receive standard oncology care as deemed appropriate by the treating physician.
- The compulsory detention for the treatment of either a psychiatric or physical (e.g. infections disease) illness.
- There is clear evidence of progressive disease.

In previous studies with pembrolizumab in solid tumors there has been transient increase in lesion size due to inflammatory immune response followed by clear evidence of lesion regression. Therefore, CAT scan evidence of progression in the global tumor burden will not be criteria for discontinuation or by itself deemed evidence of progression on therapy. It is possible index tumor may enlarge > 25% or new lesions appear after 2 doses pembrolizumab before repeat CAT scan. Surgical staging at time of resection will verify progression or whether robust inflammatory response was misinterpreted as progression on repeat CAT scans.

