20.5 Immediate Reporting of Serious Adverse Events

20.5.1 Serious Adverse Events

A serious adverse event is any adverse event occurring at any dose or during any use of Merck's product that:

- Results in death;
- Is life threatening;
- Results in persistent or significant disability/incapacity;
- Results in or prolongs an existing inpatient hospitalization;
- Is a congenital anomaly/birth defect;
- Is another important medical event
- **Note:** In addition to the above criteria, adverse events meeting either of the below criteria, although not serious per ICH definition, are reportable to the Merck in the same timeframe as SAEs to meet certain local requirements. Therefore, these events are considered serious by Merck for collection purposes.

- Is a new cancer (that is not a condition of the study);
- Is associated with an overdose.

Refer to Table 6 for additional details regarding each of the above criteria.

For the time period beginning when the consent form is signed until treatment allocation/randomization, any serious adverse event, or follow up to a serious adverse event, including death due to any cause other than progression of the cancer under study that occurs to any subject must be reported within 24 hours to the Duke Sponsor (DCI Safety Desk) who will report within 2 working days to Merck Global Safety if it causes the subject to be excluded from the trial, or is the result of a protocol-specified intervention, including, but not limited to, washout or discontinuation of usual therapy, diet, placebo treatment or a procedure.

For the time period beginning at treatment allocation/randomization through 90 days following cessation of treatment, or 30 days following cessation of treatment if the subject initiates new anticancer therapy, whichever is earlier, any serious adverse event, or follow up to a serious adverse event, including death due to any cause other than progression of the cancer under study whether or not related to the Merck product, must be reported within 24 hours to the Duke Sponsor (DCI Safety Desk) who will report within 2 working days to Merck Global Safety.

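### Sections 13.2 and 15.1 make no exception for the planned adjuvant chemotherapy and so contradict the sections that give adjuvant pembrolizumab after it

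*Combined protocol and SAP*

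**What the plan says.** **Sections that build chemotherapy into the sequence.** Section 3.1 lists up to four cycles of standard adjuvant chemotherapy under the treatment groups. Section 11.1 has patients evaluated and "offered adjuvant chemotherapy based on standard criteria such as T > 3 cm", among other criteria. Section 9.8 then says: "Following completion of all standard adjuvant therapy, including chemotherapy and/or radiation therapy, patients will receive 4 cycles of pembrolizumab". Section 5.0 describes the same order. Appendix A gives standard adjuvant therapy its own column and sets start windows for adjuvant pembrolizumab in patients who have had chemotherapy.

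**Sections that remove patients.** Section 15.1 lists reasons for which a subject must be discontinued. One is: "The patient, for any reason, requires treatment with another systemic agent potentially effective for treatment of the study indication". It continues: "In this case, discontinuation from the study occurs immediately upon introduction of the new agent". Section 13.2 prohibits, during the screening and treatment phase, "Antineoplastic systemic chemotherapy or biological therapy". Subjects who, in the investigator's judgment, "require the use of any of the aforementioned treatments for clinical management should be removed from the trial". The radiation bullet in that list exempts post-operative radiation. The first chemotherapy bullet has no such exemption, while a later bullet bans only chemotherapy that the protocol does not specify.

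**Follow-up and safety windows.** For subjects who discontinue for reasons other than progression, 15.1 ends disease-status follow-up when a non-study cancer treatment begins. Section 27.1 follows all registered patients for response, disease-free survival and overall survival. Section 9.6 follows adverse events above grade 1 until they resolve or "until the beginning of a new anti-neoplastic therapy, whichever occurs first", and 9.8.5 is similar. Section 20.5.1 shortens the serious adverse event window to "30 days following cessation of treatment if the subject initiates new anticancer therapy, whichever is earlier", and 20.6 does the same for events of clinical interest. Section 19.3.3 moves a subject into survival follow-up once new anti-cancer therapy starts.

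**The concern.** Adjuvant chemotherapy is a systemic treatment for the study indication, and it is introduced after surgery. On its plain words, 15.1 takes the patient off study on the day it starts, whereas 9.8 has the same patient return for four cycles of pembrolizumab. A site following 15.1 and a site following 9.8 would handle identical patients in opposite ways.

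Three outputs are at stake:

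- **Adjuvant-phase data.** Adverse events under adjuvant pembrolizumab, and Collection 4 as a measure after it, would come only from patients without chemotherapy. Chemotherapy is offered on tumour size and nodal status, so these patients are a selected group.
- **Disease-free survival.** If chemotherapy counts as non-study treatment, disease-status follow-up of chemotherapy-treated patients stops soon after surgery. Censoring at that point depends on prognosis.
- **Consistency across sites.** Who contributes to these outputs would depend on which section a site followed.

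**Working it through.** The plan gives no figure on this point, so the check is mainly a comparison of texts.

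1. **Does 15.1 conflict with the sequence on its own?** Yes. Its trigger is any reason and its consequence is discontinuation from the study. Other bullets in the same list speak of leaving study treatment (the 21-day delay) or protocol therapy (bulky adenopathy), so the list itself separates leaving the study from stopping the drug.

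2. **Does 13.2 settle it?** No. Its first bullet covers all antineoplastic chemotherapy. Its later bullet implies that protocol-specified chemotherapy is allowed. Whether adjuvant chemotherapy is protocol-specified is itself unclear: 3.1 lists it as part of the single-arm treatment, while 5.0 and 11.1 say it is not specific to the study.

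3. **Does the ban end before chemotherapy?** The treatment phase is not defined. Section 3.1 puts active treatment at about 10 to 17 months. The pre-operative period runs to day 56 at most, and the adjuvant pembrolizumab cycles run from day 1 to day 64: 56 + 64 = 120 days, about 4 months. The stated duration therefore appears to include the interval in which chemotherapy is given.

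4. **How many patients could be affected?** Section 6.2 requires a primary tumour of at least 3 cm, and 11.1 uses a size above 3 cm as an example criterion, so most resected patients could be offered chemotherapy. An offer is not uptake, and uptake is not stated. As an illustration, assume that the 80% reference rate in 27.1 applies to the 30 evaluable patients: 0.80 × 30 = 24 resected. If the removal rules are applied literally, at most 24 × (1 − uptake) can still reach adjuvant pembrolizumab:

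| Assumed chemotherapy uptake | Patients who can still reach adjuvant pembrolizumab |
|---|---|
| 0% | 24 |
| 25% | 18 |
| 50% | 12 |
| 75% | 6 |
| 100% | 0 |

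These are upper limits, because 9.6 also takes patients with positive margins or N2 disease off protocol.

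5. **What is not touched?** Surgery feasibility is settled at surgery, in eligible patients with at least one dose (27.1). Objective response is assessed after neoadjuvant treatment (17.1). Pathologic response and tumour-infiltrating lymphocytes come from the surgical specimen. Collections 1 to 3 precede adjuvant chemotherapy (10.1).

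6. **What is touched?** Collection 4, adjuvant-phase adverse events and disease-free survival follow-up. Section 10.1 allows Collection 4 at the end-of-study visit if no adjuvant pembrolizumab was given, but that sample cannot measure the effect of adjuvant pembrolizumab. Overall survival is less exposed, because 19.3.3 keeps survival follow-up going.

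**The case against.** The strongest reply is that the intent is plain. Sections 3.1, 5.0, 9.8, 11.1 and Appendix A are specific and sequence chemotherapy before pembrolizumab. The later bullet of 13.2 has no function unless planned chemotherapy is allowed. Taken absolutely, the first bullet would ban pembrolizumab itself as a biological therapy. Another or new agent in 15.1 can be read as off-protocol treatment. This stands to the extent that removal is not the only reading. It does not remove the conflict: 15.1 is mandatory, carries no such limit, and nothing ranks the sections.

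Four stronger readings are tempting, and the documents do not support them.

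- **The adjuvant phase cannot be reached.** Patients who refuse chemotherapy, are not candidates, have radiation alone or have no adjuvant therapy keep a route to it (5.0, 9.6, 9.8). In the illustration the phase is empty only at 100% uptake.
- **The serious adverse event window closes before the post-operative safety period.** With a last dose on day 22, a 30-day limit falls on day 22 + 30 = day 52, while 30 days after surgery on days 29 to 56 is days 59 to 86. But the 30-day limit needs new therapy to have started, and adjuvant chemotherapy follows surgery. Until then the 90-day limit applies: 22 + 90 = day 112, beyond day 86. At most, events after a very early chemotherapy start are exposed. The death criterion in 27.1 sets its own window, and serious events considered related to pembrolizumab are reportable at any time (20.5.1).
- **All adverse event follow-up stops at chemotherapy.** Section 5.0 continues follow-up until pembrolizumab effects are grade 1 or stable, and 20.2 and 20.5.1 call for following events to outcome. The windows are inconsistent, but follow-up is not simply ended.
- **Steroids given with chemotherapy also trigger removal under 13.2.** The documents name no chemotherapy regimen or supportive medication, so this has no basis in them.

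**Conclusion.** The contradiction is real and confined to wording. Section 15.1 and the first bullet of 13.2 lack an exception for planned adjuvant chemotherapy and conflict with 3.1, 5.0, 9.8, 11.1 and Appendix A; 13.2 is also inconsistent within itself. Applied literally, these rules would remove the chemotherapy-treated subset before adjuvant pembrolizumab and could cut its disease-free survival follow-up short, against 27.1. The size depends on chemotherapy uptake and on how sites read the text, and the documents give neither. The counts above rest on an assumed 24 resected patients and on literal application. The exposed outputs are secondary, and the plan calls them exploratory; the primary analysis stands. The amendment should still be made, because the rule is mandatory and the repair is cheap.

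**What to change.** Reconcile 13.2 and 15.1, including the 15.1 sentence on disease-status follow-up, with 3.1, 5.0, 9.8, 11.1, Appendix A and 27.1. State once whether standard post-operative chemotherapy given within the protocol sequence counts as prohibited therapy, as another systemic agent, as non-study treatment or as new anti-cancer therapy. Apply that one statement to:

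- study removal (13.2, 15.1);
- disease follow-up (15.1, 27.1), with the resulting censoring rule for disease-free survival;
- the adverse event, serious adverse event and clinical-interest windows (9.6, 9.8.5, 19.3.3, 20.5.1, 20.6).

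Define the treatment phase in the same amendment. The sponsor's clinical team decides the rule; none is proposed here. The cost is a wording amendment, with no added visits, tests or patients.

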15.2 Clinical Criteria for Early Trial Termination

- Quality or quantity of data recording is inaccurate or incomplete
- Poor adherence to protocol and regulatory requirements

- Incidence or severity of adverse drug reaction in this or other studies indicates a potential health hazard to subjects
- Plans to modify or discontinue the development of the study drug

In the event of Merck decision to no longer supply study drug, ample notification will be provided so that appropriate adjustments to subject treatment can be made.

15.3 Subject Replacement Strategy

Subjects may be replaced during this study if they did not receive pembrolizumab for any reason. Otherwise replacement decisions will be made between the sponsor and investigator on a case-by-case basis.

15.4 Discontinuation of Study

This study can be terminated at any time for any reason by the PI-sponsor or the IRB. If this occurs, all subjects on study should be notified as soon as possible. Additional procedures and/or follow up should occur in accordance with Section 15.1 which describes procedures and process for prematurely withdrawn patients.

16.0 LABELING, PACKAGING, STORAGE, AND RETURN OF CLINICAL SUPPLIES

Merck Pharmaceuticals will provide pembrolizumab at no cost for this study.

16.1 Investigational Product

Pembrolizumab is a potent and highly selective humanized me of the IgG4/kappa isotype designed to directly block the interaction between PD-1 and its ligands, PDL1and PD-L2.

The investigator shall take responsibility for and shall take all steps to maintain appropriate records and ensure appropriate supply, storage, handling, distribution and usage of investigational product in accordance with the protocol and any applicable laws and regulations.

Clinical Supplies will be provided by Merck as summarized in Table 3.

Table 3 Product Descriptions

Product Name & Potency	Dosage Form
Pembrolizumab 50 mg	Lyophilized Powder for Injection
Pembrolizumab 100 mg/ 4mL	Solution for Injection

16.2 Packaging and Labeling Information

Clinical supplies will be affixed with a clinical label in accordance with regulatory requirements. Pharmacist will receive open label packages of the drug.

16.3 Clinical Supplies Disclosure

This trial is open-label; therefore, the subject, the trial site personnel, the Sponsor and/or designee are not blinded to treatment. Drug identity (name, strength) is included in the label text; random code/disclosure envelopes or lists are not provided.

16.4 Storage, Handling and Disposal

Clinical supplies must be stored in a secure, limited access location under the storage conditions specified on the label.

As with all injectable drugs, care should be taken when handling and preparing pembrolizumab. Whenever possible, pembrolizumab should be prepared in a laminar flow hood or safety cabinet using standard precautions for the safe handling of intravenous agents applying aseptic technique. Latex gloves are required. If pembrolizumab concentrate or solution comes in contact with skin or mucosa, immediately and thoroughly wash with soap and water. After final drug reconciliation, unused pembrolizumab solution should be disposed at the site following procedures for the disposal of anticancer drugs.

16.5 Dispensing

It is the responsibility of the investigator to ensure that pembrolizumab is only dispensed to study subjects. The pembrolizumab must be dispensed only from official study sites by authorized personnel according to local regulations. Clinical supplies may not be used for any purpose other than that stated in the protocol.

16.6 Drug Ordering and Accountability

16.6.1 Initial and Re-Supply Orders

Following submission and approval of the required regulatory documents, a supply of pembrolizumab may be ordered from Merck. Refer to the pharmacy manual for product ordering.

16.6.2 Pembrolizumab Accountability

It is the responsibility of the investigator to ensure that a current record of pembrolizumab disposition is maintained at each study site where pembrolizumab is inventoried and disposed. This inventory must be available for monitoring. Records or logs must comply with applicable regulations and guidelines, and should include:

- Amount received and placed in storage area.
- Amount currently in storage area.
- Label ID number or batch number and use date or expiry date.
- Dates and initials of person responsible for each pembrolizumab inventory entry/movement.
- Amount dispensed to and returned by each subject, including unique subject identifiers.
- Amount transferred to another area/site for dispensing or storage.
- Non-study disposition (e.g., lost, wasted, broken).
- Amount destroyed at study site.

All supplies, including unused, partially used or empty containers will be destroyed according to sites drug destruction policy.

16.6.3 Pembrolizumab Returns and Reconciliation

The investigator is responsible for keeping accurate records of the clinical supplies received from Merck or designee, the amount dispensed to and returned by the subjects and the amount remaining at the conclusion of the trial.

Upon completion or termination of the study, all unused and/or partially used investigational product will be destroyed at the site per institutional policy. It is the Investigator's responsibility to arrange for disposal of all empty containers, provided that procedures for proper disposal have been established according to applicable federal, state, local and institutional guidelines and procedures, and provided that appropriate records of disposal are kept.

